
 • Collect uptake data on use of text messages with health educator and attendance at community sessions • Track participant use of text-Web components • Conduct N~20 stakeholder interviews with participants to assess perceptions of human interaction in intervention delivery (5 intervention arm; 5 control arm; 10 utilizers of texting with health educator or community sessions) 	
 • Perception and uptake of intervention components, electronic or otherwise • Women's health literacy, screening/risk reduction outcomes. 	
 • Participant tracking and collection of intervention component uptake data to occur between Y2-Y5 • Key stakeholder interviews conducted between Y3Q4-Y4Q1 • Manuscript #6 perceptions of role of human interaction in intervention delivery in Y4 • Manuscript #7 uptake of text-Web components among high-risk women in Y5 • Manuscript #8 impact of human interaction (uptake of text messaging with health educator and/or attendance at community sessions) on women's health literacy and screening/risk reduction in Y5
--	--	--

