Power. The sample size for the Aim 1 feasibility study is based on our original SHE study pilot and expanded to allow for rigorous testing and refining of modality.²⁶ The sample size of N~200 for the Aim 2 RCT was determined to provide satisfactory power ($\geq 80\%$) for this study in addressing the specific aims, which depends on the following parameters: number of participants (n), number of measurements (t=3 for health literacy for screening; t=4 for screening/risk reduction practices), effect size (f) as group difference in change, correlation between repeated measures (r), and attrition rate. The effect sizes estimated from the original SHE study were in the small to moderate range—for health literacy (8 domains), average $f=0.13$ at immediately post-intervention and 0.16 at 1-year post-intervention; $f=0.17$ for cervix screening and 0.12 for condom use during the last intercourse at 1-year post-intervention. Although effect sizes for breast cancer screening and STI screening are not available from the original SHE study, we expect similar, small to moderate effect sizes for these outcomes. Thus, we conservatively assumed the smallest observed effect size of $f=0.12$ for our power calculation. The correlations between repeated measures observed in the original SHE study were $r=0.46$ on average, with the range of 0.39-0.75 between baseline and immediately post-intervention and 0.25-0.61 between baseline and 1-year post-intervention. Power analysis of these data ($f=0.13$, $t=3$ or 4, $r=0.46$) and G*Power 3.1.9.2 indicated that a sample of 124 women will produce $\geq 80\%$ power for both health literacy (80%) and screening/risk reduction behaviors (85%). In our original SHE study, the 3-year follow-up rate was 85%. Conservatively assuming a high attrition rate up to 40%, we will recruit ~200 women at baseline to adequately power the SHE-Women study—i.e., maintain $\geq 80\%$ power even with a low follow-up rate as small as 60%. As

Table 4. Expected attrition over study period

	Aim 1 feasibility Target N~20	Aim 2 RCT Target N~200	Aim 3 (same as Aim 2)
Consent and baseline	20	260	--
Intervention initiation	15	220	--
Post-intervention	10	200	--
1 year follow-up	--	170	--
2-year follow-up	--	160	--
3-year follow-up	--	150	--

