described above, missing data due to either attrition or nonresponse will be fully recovered via multiple imputation in our intent-to-treat analysis, which will provide additional power and remove any confounding effect of missing data on our statistical power. For Aim 3, the key stakeholder interviews will occur with enough research participants to reach thematic saturation. Based on prior experience with key stakeholder interviews, we believe N~20 interviews will accomplish this goal,²⁷ but have resources to interview additional participants. Additionally, our COVID-19 module interview suggests N~30 interviews will accomplish the goal of thematic saturation.

Outcomes and instruments. Aim 1 feasibility outcomes include uptake of intervention components, barriers and facilitators of implementation, problems with delivery, and necessary modifications.⁴⁵ Pilot effectiveness outcomes will include an assessment of women's health literacy, operationalized as knowledge, beliefs, and self-efficacy for screening related to cervical, breast cancer, birth control, and STIs, post-intervention.^{4,26} Aim 2 RCT outcomes include women's health literacy, immediately post-intervention and 1-year post-intervention; and screening/ risk reduction for cervical, breast cancer, unintended pregnancy, and STIs at 1, 2, and 3-years post-intervention. Aim 3 outcomes include perception and uptake of intervention components.⁴⁵

Feasibility and perception of intervention outcomes are defined below and assessed through participant tracking and key stakeholder interviews with a subset of participants.:

- *Uptake of integrated, multimedia electronic women's health literacy intervention:* documentation of number of participants who responded to text messages; clicks on Website; real-time assessment of knowledge; time elapsed between text messages and Website clicks; number of outreach messages (through text, phone, or Facebook); Facebook posts/messages; chats with health educator; total minutes of contact through text, Web, chat, Facebook with each participant; attendance at community sessions
- *Barriers and facilitators of implementation:* problems described by participants in setting up text message platform, Website, closed Facebook group; factors that make set up of text message platform, Website, closed Facebook group ease of use; ease of Website components use (content modules, assessments)

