Using quantitative data from the pilot trial of the SHE-Women text-Web intervention, we will conduct descriptive analysis and bivariate tests to explore women's health literacy (knowledge, beliefs, and self-efficacy) for screening related to cervical, breast cancer, birth control, and STIs (Aim 1). The results including effect sizes estimated for the outcome will be utilized for refinement of the intervention content and modality. To test the hypothesis that SHE-Women will be more effective than standard of care at improving outcomes (Aim 2), we will utilize mixed modeling techniques for repeated measures, separately for each outcome variable: health literacy for screening and screening/risk reduction practices. General/generalized models will evaluate the effects of the intervention by estimating overall group difference across measurements (i.e., group effect), change over time (i.e., time effect), and group difference in change (i.e., group-by-time interaction). In other words, we will evaluate whether the intervention vs. control group improves in outcomes over time. The models will account for the impacts of sociodemographic characteristics as well as other cross-cutting risk factors including tobacco use, alcohol use, criminal justice involvement, intimate partner violence, lack of continuous health care coverage or primary care contact, etc. (covariates), thereby providing unbiased estimates of the intervention effects. The models for screening/risk reduction behaviors will also consider knowledge about cervix cancer, breast cancer, birth control, or STI as an additional covariate for the respective outcome variable. Incorporating participant tracking data, descriptive analysis and bivariate tests will demonstrate the pattern and uptake of various intervention components as measured by number of participants who responded to text messages; clicks on the Website; interactive clicks on the Website, e.g. through real-time assessment of knowledge; time elapsed between text messages and Website clicks; number of outreach messages (through text, phone, or Facebook); Facebook posts/messages; chats with health educator; total minutes of contact through text, Web, chat, Facebook with each participant; and attendance at community sessions (Aim 3). General/generalized mixed modeling for repeated measures will assess the impacts of the uptake on each outcome variable of health literacy for screening and screening/risk reduction practices while controlling for the impact of sociodemographic characteristics and other risk factors. A proper covariance structure for repeated measures will be chosen for each outcome variable based on model fit (i.e., likelihood, Akaike Information Criterion, adjusted Bayesian Information Criterion). Statistical significance will be determined at 0.05 alpha level, and all analyses conducted using SAS 9.4⁵⁹

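### The Aim 3 uptake models do not say how the baseline value of the outcome enters, so an uptake main effect would count pre-existing differences between users and non-users as an effect of uptake

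*Combined protocol and SAP*

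**What the plan says.** The only inferential sentence for Aim 3, in Data analysis, states that general or generalized "mixed modeling for repeated measures will assess the impacts of the uptake on each outcome variable" of literacy and screening/risk reduction, "while controlling for the impact of sociodemographic characteristics and other risk factors". It names no baseline covariate and does not say which model term is the impact.

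The Aim 2 text in the same paragraph is more specific. It lists a group effect, a time effect and "group difference in change (i.e., group-by-time interaction". It also says: "The models for screening/risk reduction behaviors will also consider knowledge about cervix cancer, breast cancer, birth control, or STI as an additional covariate". No time point is given for that knowledge score.

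Baseline is part of the outcome series. Power counts "t=3 for health literacy for screening; t=4 for screening/risk reduction practices". Outcomes and instruments lists only two post-baseline times for literacy and three for screening: "immediately post-intervention and 1-year post-intervention; and screening/ risk reduction for cervical, breast cancer, unintended pregnancy, and STIs at 1, 2, and 3-years post-intervention". Data collection confirms a baseline survey.

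Uptake is not randomized. Under Intervention arms and procedures, access to content depends on the user's engagement. Under Opportunities for human interaction, texting and community sessions are offered to both arms. Compensation and retention expects about half to accept. Table 3 has uptake tracked from Year 2 to Year 5 and plans Manuscript #8 on the "impact of human interaction (uptake of text messaging with health educator and/or attendance at community sessions".

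**The concern.** Women who choose to text the educator, attend sessions or open content may differ at baseline from those who do not, in literacy or in screening status. Randomization does not balance users against non-users. The baseline value of the outcome is an obvious candidate confounder, and it is collected in the baseline survey, yet the plan does not say how it is used.

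Two problems follow if the sentence is implemented as an uptake main effect over all visits. First, a value recorded before any uptake is regressed on later uptake. Second, differences that persist from baseline to follow-up are read as results of uptake. A third issue is timing: uptake tracked over Years 2 to 5 overlaps outcome follow-up, so a total count can include contact that came after the outcome it is meant to explain.

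At stake is the answer to how much human contact an electronic intervention needs, which the protocol lists among its key findings. The randomized Aim 2 comparison is not affected by this point.

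**Working it through.** **1. Is baseline in the outcome vector?** Literacy: 2 post-baseline times + 1 baseline = 3, matching t=3. Screening/risk reduction: 3 + 1 = 4, matching t=4. So yes.

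**2. Is it adjusted for or contrasted against in Aim 3?** Nothing in the Aim 3 sentence says so. The examples of risk factors given for Aim 2 are tobacco, alcohol, criminal justice involvement, partner violence, and health care coverage or primary care contact, with an open-ended ending. The knowledge covariate appears in the Aim 2 text, covers only the screening models and is not the baseline value of the screening outcome.

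**3. What could this do?** The plan gives no Aim 3 figure to reproduce, so this is an illustration.

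Inputs:
- From Power: r = 0.46 and N of about 200.
- From Compensation and retention: about half with high uptake.
- From Data analysis: alpha 0.05 (taken as two-sided; the plan does not say).
- Assumed: uptake-baseline correlation ρ = 0.2 (range 0.1 to 0.3), a continuous outcome in SD units, equal correlation between all visits, complete data, no true uptake effect.

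With uptake split at its median, the baseline gap between users and non-users is 2·√(2/π)·ρ = 1.596 × 0.2 = 0.319 SD.

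*Mechanism A: uptake depends only on the observed baseline score.* The gap at each later visit is 0.46 × 0.319 = 0.147.
- Main effect over all visits, t=3: 0.319 × (1 + 2×0.46)/3 = 0.204. At t=4: 0.319 × (1 + 3×0.46)/4 = 0.190.
- Change from baseline: 0.147 − 0.319 = −0.172.
- Post-baseline visits with baseline as covariate: 0.

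*Mechanism B: uptake follows a stable trait that also drives the outcome.* The gap is 0.319 at every visit.
- Main effect over all visits: 0.319 at t=3 and t=4.
- Change from baseline: 0.
- Post-baseline visits with baseline as covariate: about 0.319 × (1 − 0.46) = 0.172.

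A simulation (N=200, t=3, ρ=0.2, 2,000 replicates) agrees:

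| Term read as the impact | A: mean estimate (SD) | A: false positives | B: mean estimate (SD) | B: false positives |
|---|---|---|---|---|
| Uptake main effect, all visits | 0.20 | 44% | 0.32 | 82% |
| Uptake-by-time (change from baseline) | −0.17 | 29% | 0.00 | 5% |
| Post-baseline visits, baseline as covariate | 0.00 | 5% | 0.18 | 42% |

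For ρ = 0.1 and 0.3 the simulated all-visit main effect is 0.10 and 0.31 SD under A, and 0.16 and 0.48 SD under B. At ρ = 0 every approach rejects about 5% of the time. Results at t=4 are similar.

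The all-visit main effect is biased under both mechanisms. The baseline covariate removes the bias under A and roughly halves it under B. The change contrast removes it under B but gives a bias of opposite sign under A.

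**The case against.** The strongest reply is that the plan is silent, not wrong. Baseline is already among the repeated measurements, and for the same model family Aim 2 is read through group-by-time. If Aim 3 is read through uptake-by-time in the same way, stable baseline differences are separated from change; under mechanism B the false-positive rate is then 5%. This stands in part. A reader might infer that the models definitely leave baseline out, and the documents do not support that: they leave the term unspecified. But the Aim 3 sentence does not adopt the Aim 2 contrast, and under mechanism A that contrast is itself biased.

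A second reply is that other risk factors might include baseline screening status. The protocol's Background text describes the Table 1 items generally as women's health risk factors, and these include no recent Pap test and no condom use at last sex. The wording does not exclude this. Table 1 keeps such items apart from its cross-cutting block, however, and contains no literacy scores, so baseline literacy would still be unaddressed.

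Third, the direction is open. A reader might infer that uptake will be made to look effective. Nothing in the documents shows that. Texting is offered to women who have questions, which may attract the less informed. Women who do not open content are contacted again, and the number of outreach messages is itself an uptake measure, so that count can be higher in less engaged women. The bias could run against uptake. This stands, and is why no direction is claimed.

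Fourth, a baseline covariate is not a full cure, as mechanism B shows (42% false positives). This also stands. Defining uptake as time-varying and zero at baseline would stop the baseline outcome being regressed on later uptake, but would not remove self-selection.

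**Conclusion.** The point holds as a gap in specification. The plan calls its Aim 3 estimates impacts of a self-selected exposure, without stating any adjustment for, or contrast against, the baseline value of the outcome. On the literal main-effect reading, pre-existing differences are attributed to uptake.

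The real size and direction cannot be derived, because no uptake-baseline correlation is given. The 0.20 to 0.32 SD figure rests on the assumed correlation of 0.2, r=0.46 at all visits, a median split and no true effect. The bias does not depend on N; the false-positive rates do, and were computed for 200 women with complete data.

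The illustration concerns literacy-type scores. A reader might also want a carry-over figure for Pap status. That would need an invented starting gap and an assumption about new screening during year 1, neither of which the documents supply for users and non-users, so none is offered.

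The change should be made before the Aim 3 analysis. The choice of term can change the sign of the answer, and choosing it after seeing the data would be hard to defend.

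**What to change.** In the Aim 3 part of Data analysis:

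- Fit the uptake models to post-baseline visits, with the baseline value of the same outcome as a covariate in each.
- Count only uptake that occurred before each outcome assessment.
- Add the uptake-by-time (change from baseline) contrast as a sensitivity analysis, and say that neither approach is unbiased under every selection mechanism. Agreement between the two would be reassuring; disagreement should be reported as such.
- In Manuscript #8, report the uptake coefficients as adjusted associations, not impacts.

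The baseline survey and uptake tracking are already planned, so no new data or visits are needed. The cost is slightly more analysis work, including linking uptake dates to assessment dates, and a weaker causal claim.

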
organizations (i.e. transitional living facilities, DV shelters, social support centers, etc.)
 
 • Randomize participants to intervention and control arms • Deliver SHE-Women to N~100 women via text-Web platform; deliver standard of care discharge planning session to N~100 women • Conduct baseline, post-intervention, 1, 2, 3 year assessments of women's health literacy and screening/risk reduction outcomes • Conduct N~30 stakeholder interviews to determine efficacy of COVID-19 module 	
 • Screening/risk reduction for cervical, breast cancer, unintended pregnancy, STIs and COVID-19 	
 • Manuscript #2 strategies for recruiting women leaving jails into health promotion interventions in Y3 • Conduct follow-ups for 3 years from intervention during Y1-Y5/ maintain 75-85% follow-up rate • Manuscript #3 effectiveness of SHE-Women at improving women's health literacy in Y3 • Manuscript #4 effectiveness of SHE-Women at improving women's health screening/risk reduction in Y4 • Placement of SHE-Women on NCI Research-Tested Intervention Programs site in Y5 • Manuscript #5 3-year outcomes of interventions in Y5
---	---	--

Aim 3. Understand the role and impact of human interaction in electronic interventions by tracking participants and interviewing key stakeholders.

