- *Potential problems with delivery of intervention:* number of incorrect phone numbers, changed phone numbers; problems with Website described by participants and staff; description of level of annoyance with outreach messages through text, phone, and Facebook; number of participants re-incarcerated during intervention trial and, thus, resulted in non-completion; problems with chat feature with health educator
- *Modifications needed to maximize implementation:* suggestions from participants about improving multimedia electronic approaches; suggestions about improving real-time assessments of knowledge
- *Perception of human interaction in intervention:* positive and negative aspects of multimedia electronic educational interventions; benefits and disadvantages to offer of community-based sessions; perceived value of human face in video/audio intervention content; advantages/disadvantages of conversation during discharge planning session for control arm

Women's health literacy and screening/risk reduction outcomes are described in Table 5 below. Items will be adapted from scales listed in Table 5.

Table 5. Women's health literacy and screening/risk reduction outcomes and instruments	
Women's health literacy (Knowledge, beliefs, self-efficacy, confidence navigating systems)	Screening/ Risk reduction
Cervix literacy Pap knowledge scale ⁴⁶ Health belief model scale for cervical cancer and Pap smear test ⁴⁷ Self-efficacy for cancer screening scale ⁴⁸ Confidence navigating health systems scale (cervix, breast, birth control, STI) ⁴	Up-to-date Pap exam or HPV co-testing Abnormal Pap follow-up HINTS cervical cancer screening questions ⁴⁹ Original SHE HPV co-testing and abnormal Pap follow-up questions ⁴
Breast literacy Knowledge, beliefs, self-efficacy items from breast cancer literacy assessment ⁵⁰	Up-to-date screening mammography (biennial) for age 50+ HINTS breast cancer screening questions ⁴⁹
Birth control literacy Contraceptive knowledge assessment ⁵¹ Beliefs about acquisition and use of contraceptive items from self-efficacy scale ⁵²	Current use of hormonal or long-acting reversible birth control method, if no menopause or sterilization BRFSS birth control questions ⁵³
Sexually transmitted infection literacy STD knowledge questionnaire ⁵⁴ Multidimensional condom attitudes scale ⁵⁵ Condom self-efficacy scale ⁵⁶	Condom use at last sex STI treatment BRFSS condom use and STI treatment questions ⁵³

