
Missing data will be handled by iterative Markov Chain Monte Carlo (MCMC) multiple imputation, in which expectation-maximization (EM) algorithm provides prior estimates of missing values for subsequent MCMC procedure.⁶⁰ A large number of (e.g., 200) imputed datasets will be generated and then analysis results from each imputed dataset will be combined together to make valid statistical inference. This approach includes all selected variables (auxiliary variables) into the imputation process, which allows for greater recovery of missing data.⁶¹ It is possible that some women will reenter the jail facility during the recruitment period. To avoid re-randomizing these same participants, we will collect basic identifying information recruitment (name, DOB, race) and double check to see if the participant already is enrolled in our study.

Integration of study aims to meet project objective. Because the objective of this study is to ultimately create a sustainable model for dissemination of health promotion interventions for vulnerable populations, we feel it is important to use a mixed methods approach to understand the relationship between qualitative and quantitative data.⁶² Integration of study aims to meet our project objective will primarily occur through the writing of Manuscripts # 1,6 and 8 (see Table 3). In each of these manuscripts we plan to report on both the perceptions of key stakeholders, as well as the effectiveness of the intervention given the electronic modality of delivery. We will take lessons learned to develop subsequent projects that test SHE-Women in diverse groups of high risk women both inside and outside our catchment area.

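### The single EM-then-MCMC imputation does not suit the yes/no screening outcomes: its fractional values need an unstated further step, and rounding them would bias the arm difference

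*Combined protocol and SAP*

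**What the plan says.** The missing-data paragraph under Data analysis gives one method for all missing data: "Missing data will be handled by iterative Markov Chain Monte Carlo (MCMC) multiple imputation". Starting estimates for the chain come from an EM step. On the contents of the imputation model it says "This approach includes all selected variables (auxiliary variables) into the imputation process", and on the number of imputations "A large number of (e.g., 200) imputed datasets will be generated". SAS 9.4 is the named software.

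For Aim 2, Data analysis plans repeated-measures mixed models, separately for each outcome: "General/generalized models will evaluate the effects of the intervention". The right-hand column of Table 5 lists outcomes that are yes/no in substance, among them "Up-to-date Pap exam or HPV co-testing" and "Condom use at last sex", as well as mammography at age 50 and over and current use of certain birth control methods.

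The Power section relies on this imputation to recover all missing data in the intent-to-treat analysis. The plan does not state a distribution for the imputation model, a method for binary variables, any rounding rule, a link function, or whether arm is in the imputation model.

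**The concern.** An EM step followed by MCMC is the usual form of joint multivariate normal imputation. Applied to a 0/1 variable it gives values such as 0.63 or 1.2. A linear mixed model accepts these; a mixed model with a binary distribution does not. Something must therefore happen between imputation and analysis, and the plan does not say what. Rounding to 0 or 1 is the obvious improvisation, and it distorts proportions by an amount that depends on the prevalence and on the residual variance used for the draw. Because the arms differ in prevalence, the distortion does not cancel between them.

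Screening and risk reduction is one of the two Aim 2 effectiveness outcomes. The Power section expects small effects (f = 0.12 to 0.17), and a sizeable share of late outcomes would be imputed. The estimated effect could then move because of a programming choice made after the data are in.

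**Working it through.** The plan gives no figure for imputation error, so there is none to reproduce.

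**Inputs from the documents**
- Missing at years 1, 2 and 3 (Table 4: 170, 160 and 150 seen). Of the target 200: 15%, 20%, 25%. Of the 260 consented, who are randomised after consent: 90/260 = 35%, 100/260 = 38%, 110/260 = 42%. The Power section's own worst case is 40%.
- Prevalence (Table 1, parent study): 22.6% had no recent Pap test, so about 77.4% were up to date; 75.1% used no condom at last sex, so about 25% did.
- Equal arms: "Deliver SHE-Women to N~100 women via text-Web platform", and about 100 controls.

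**Assumptions, not in the documents:** intervention-arm rates of 90% (Pap) and 40% (condom); rounding at 0.5.

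**1. Values outside 0 to 1.** With p = 0.774, s = √(0.774 × 0.226) = 0.418.
- P(draw > 1) = Φ(−0.226/0.418) = 0.294
- P(draw < 0) = Φ(−0.774/0.418) = 0.032
- Total: about 33%

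**2. Rounding, one joint model with arm.** A draw rounds to 1 with probability Φ((p − 0.5)/s), where s is the pooled residual SD. The final difference is (1 − m) × true + m × imputed, with m the fraction missing.
- Pap: s = √((0.1749 + 0.0900)/2) = 0.364. The imputed rates are Φ(0.274/0.364) = 0.774 and Φ(0.400/0.364) = 0.864, a difference of 9.0 points instead of 12.6. At m = 0.25: 0.75 × 12.6 + 0.25 × 9.0 = 11.7 (7% too small). At m = 0.42: 0.58 × 12.6 + 0.42 × 9.0 = 11.1 (12% too small).
- Condom: s = √((0.1875 + 0.2400)/2) = 0.462. The imputed rates are 0.294 and 0.414, a difference of 12.0 points instead of 15. At m = 0.25: 14.25 (5% too small). At m = 0.42: 13.7 (8% too small).

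**3. Dropout mildly tied to baseline status.** Large-sample simulations, baseline in the imputation model, log odds ratio of follow-up on baseline 1.5.
- Pap: about 11.5 at 25% missing (9% too small) and 10.6 to 10.8 at 42% (14-16%).
- Condom: about 14.4 at 25% (4%) and 13.5 to 14.0 at 42% (10% down to 7%).

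**4. Rounding, arms imputed separately.** Each arm now has its own s.
- Pap: Φ(0.274/0.418) = 0.744 and Φ(0.400/0.300) = 0.909, a difference of 16.5 points. At m = 0.25: 13.6 (8% too large). At m = 0.42: 14.2 (13% too large).
- Condom: imputed difference 13.7. At m = 0.42: 14.5 (4% too small).

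**5. Comparators.** A second set of large simulations used four waves, assumed 10-point differences (77 v 87%, 25 v 35%, 52 v 62%) and dropout unrelated to outcome. The share of the true log odds ratio retained was:

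| Imputation | 25% missing at year 3 | 40% missing |
|---|---|---|
| Logistic, arm included | 99-101% | 99-101% |
| Normal, arm included, unrounded | 99-101% | 99-101% |
| Normal, arm included, rounded | 91-95% | 84-91% |
| Normal, arm omitted, rounded | 76-78% | 57-60% |

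The last row is poor mainly because arm is missing from the model, not because of rounding.

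**The case against.** The strongest reply is that the harm is hypothetical. The text names neither a normal distribution nor rounding nor a logistic link. A binary imputation model, or a linear analysis of unrounded values, would fit the words as they stand. Unrounded normal draws with arm included are close to unbiased when dropout is unrelated to outcome. The assumed 90% and 40% rates are not the plan's, and 42% missing needs all 260 consented women in the intent-to-treat set; at the planned 75-85% follow-up the distortion is modest.

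Most of this stands, and it limits the point. A reader might infer that the plan prescribes normal imputation with rounding, and that the intervention effect will therefore be attenuated. The documents do not support that: normality is implied, rounding is nowhere mentioned, and the direction reverses for the Pap contrast if the arms are imputed separately. Nor do they support extending the point to literacy scales, which are unaffected when analysed as continuous.

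What the reply does not remove is the mismatch. One method is given for all variables, its natural reading yields values that a binary model cannot use, and nothing fills the gap. Unrounded values are also not always safe: with dropout tied to baseline status, one run lost 5-10% of the log odds ratio for 77 v 87%.

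**Conclusion.** The concern holds as a conditional one. The stated imputation, on its natural reading, does not fit the yes/no outcomes in Table 5, and the plan omits the step needed to use its output in a binary-outcome model. If that step is rounding at 0.5 with arm in one joint model, the assumed differences shrink by about 4-9% at 25% missing and about 8-16% at 42% missing (one run of the condom contrast gave 7%). If the arms are imputed separately, the Pap difference grows by about 8-13%. These sizes rest on the assumed follow-up rates, the 0.5 cut-off, and dropout that is random or depends only mildly on baseline. Without rounding, little or nothing is lost in most settings. The change is worth making before analysis because a better-suited method is available at small cost.

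**What to change.** In the missing-data paragraph of Data analysis, replace the method for binary outcomes with fully conditional specification using logistic models, and use regression or predictive mean matching for the scales. State that arm, all visits and the named auxiliary variables are in the imputation model, and that normal draws will not be rounded. Restrict each outcome's imputation to women in its denominator: age 50 and over for mammography, and no menopause or sterilization for birth control.

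Sparse outcomes need a reduced predictor set or a penalised or augmented logistic model. The parent study had 23 women aged 50 and over among 261; a similar sample would leave about 23 × 150/260 = 13 observed at year 3, and a full logistic imputation model could separate.

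The cost is a few sentences in the plan, somewhat longer run time, and more model checking for the sparse outcomes. No new data are needed.
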